1.1. Identification

Title	PROMISE UK
Version	Version 4.4-UK
Date	21 July 2022
History	Please refer to Table 1 below

Table 1. Revision history

Version	Date	Changes
Version 4-UK	28 November 2018	Initial version (adapted from PROMISE International version 4)
Version 4.1-UK	01 June 2020	Update product reference numbers, device description, and manufacturer Refer to IFU for procedural steps Clarify reporting of planned interventions for pre-existing conditions Update clinical data section to reference latest published information
Version 4.2-UK	31 May 2021	Update to study anticipated enrolment and completion timelines due to delays experienced due to the coronavirus pandemic. Update to current standard: ISO 14155:2020 Clarification on exiting of patients who met main study endpoint of amputation. Note that some patient follow-up imaging assessment may be unnecessary in cases where earlier occlusion endpoint had been reached, to be discussed with the study sponsor.
Version 4.3-UK	29 November 2021	Update to study anticipated enrolment and completion timelines due to impacts due to the coronavirus pandemic.
Version 4.4-UK	21 July 2022	Ongoing update to study anticipated enrolment and completion timelines due to impacts due to the coronavirus pandemic.

1.5. Principal investigators and investigation sites

The list of principal investigators and investigation sites is provided in Annex A to this protocol.

1.6. Overall synopsis of the clinical investigation

1.6.1. Objectives

The objective of this post-market study is to collect “*real-life*” clinical data among a population of patients treated with the commercially-available LimFlow System in order to evaluate the **safety and effectiveness** of the LimFlow System in creating a below-the-knee arterio-venous fistula for venous arterialization in subjects with critical limb ischaemia.

1.6.2. Design

This study is a single-arm, open-label, prospective, post-market follow-up study to be conducted on up to 25 eligible patients (roll-in subjects plus 20 analysis subjects) with a twelve-month follow-up period. This study was designed and is to be conducted in compliance with the ISO 14155 standard.

1.6.3. Endpoints

Primary endpoint

- Amputation-free survival

Secondary endpoints

- Complete wound healing
- Primary and secondary patency
- Limb salvage
- Technical and procedural success

1.6.4. Visits and exams

Patients should be followed at regular intervals during one year after the initial percutaneous deep vein arterialization procedure. The protocol follow-up schedule is intended to align with the standard of care as seen with patients who are treated with surgical bypass or endovascular revascularization. Visits and exams scheduled for this post-market study are presented in Table 2 below (keys: ■ mandatory, □ optional).

Table 2. Visits and exams

Exams	Baseline	Treatment	Week 02	Month 01	Month 02	Month 03	Month 06	Month 09	Month 12
Eligibility	■								
Demographics	■								
Infection status [†]	■								
Venous mapping [‡]	■								
Angiogram	■	■							
Ultrasound		Duplex		Duplex	Duplex	Duplex	Duplex	Duplex	Duplex
Medication	■	■	■	■	■	■	■	■	■
Creatinine	■								
Rutherford	■			■	■	■	■	■	■
WiFi	■			■	■	■	■	■	■
Wound pictures	■		■	■	■	■	■	■	■
Pain	■		■	■	■	■	■	■	■
Perfusion	□		□	□	□	□	□	□	□
Quality of Life	■					■	■	■	■

Adverse events		■	■	■	■	■	■	■	■	■
----------------	--	---	---	---	---	---	---	---	---	---

¹Wound culture and/or blood analysis (WBC, CRP, ESR)

²Phlebography, duplex ultrasound, MRV or CTV, depending on what is available

1.6.5. Inclusion criteria

- I-1. Subject must be > 21 and < 95 years of age
- I-2. Clinical diagnosis of symptomatic critical limb ischaemia, defined as Rutherford category 5 or 6
- I-3. Assessment that no conventional surgical or endovascular treatment is possible
- I-4. Proximally, the target in-flow artery at the cross-over point must be treatable with a 3.5 – 4.0 mm stent after pre-treatment (by visual estimate), and be <50% stenosed
- I-5. Subject is willing and has adequate support to comply with protocol requirements, including medication regimen and follow-up visits

1.6.6. Exclusion criteria

- E-1. Concomitant hepatic insufficiency, deep venous thrombus in target limb, uncorrected coagulation disorders, or current immunodeficiency disorder
- E-2. Life expectancy less than 12 months
- E-3. Patient currently taking coumarin/warfarin which, in the opinion of the attending physician, interferes with the patient's treatment
- E-4. Any significant medical condition which, in the attending physician's opinion, may interfere with the patient's optimal treatment
- E-5. Patient currently participating in another investigational drug or device study that has not completed the primary endpoint or that clinically interferes with the endpoints of this treatment
- E-6. Patient unable to give consent
- E-7. Pregnant or breastfeeding women
- E-8. Documented myocardial infarction or stroke within previous 90 days
- E-9. Patients suffering from renal insufficiency (GFR value less than 30 ml/min/1.73 m²) who are not on haemodialysis
- E-10. Patients with vasculitis and/or untreated popliteal aneurysms
- E-11. Patients with acute limb ischaemia
- E-12. Prior peripheral arterial bypass procedure above or below the knee which could inhibit proximal inflow to the stent graft
- E-13. Lower extremity venous disease with significant oedema in the target limb that may inhibit the procedure and/or jeopardize wound healing, in the investigator's opinion
- E-14. Known or suspected systemic or severe infection (e.g., WfI foot Infection grade of 3)
- E-15. Known or suspected allergies or contraindications to stainless steel, nickel, or contrast agent that cannot be adequately pre-treated, or patients who cannot receive anticoagulation or antiplatelet aggregation therapy
- E-16. Severe heart failure, which in the opinion of the investigator may compromise subject's ability to safely undergo a percutaneous procedure (e.g., known ejection fraction of < 40%, NYHA Classification III-IV)

2. Identification and description of the medical device

2.1. Summary description and intended purpose

The medical device is the LimFlow System, which is CE-marked and intended to treat critical limb ischaemia by minimally invasively creating an arterio-venous bypass graft to produce the venous arterialization procedure in the below-the-knee vasculature.

2.2. Populations and indications for which the device is intended

The LimFlow System is indicated for endovascular, minimally invasive procedures in patients who have a clinical diagnosis of symptomatic critical limb ischaemia, have been assessed by a vascular surgeon and interventionalist and it was determined that no surgical or endovascular treatment is possible, and are clearly indicated for major amputation—also referred as “no-option” patients.

2.3. Device identification and materials used

The LimFlow System consists of five (5) medical device components: the ultrasound system, the extension cable set, the arterial and venous catheter set, the valvulotome, and a series of stent grafts with delivery systems. Below in Table 3 is a listing of all medical device components including whether or not the devices are sterile, reusable, or in contact with patient blood, along with device names and current identification numbers (subject to change).

Table 3. Device identification

Catalogue Number	Device	Materials	Sterile	Reusable	Blood contact
LF-US-EU-XX	Ultrasound system	Aluminium (outside enclosure of transceiver box) plus computer notebook	No	Yes	No
LF-EX-EU-XX	Extension cable set	Plastic cable isolation	Yes	No	No
LF-XX-EU-XX	Arterial and venous catheters	Various plastics and metals (nitinol and stainless steel)	Yes	No	Yes
LF-VT-EU-XX	Valvulotome	Nitinol, stainless steel, and various plastics (polyimide, pebax, etc.)	Yes	No	Yes
LF-SG-DDDDLL-EU-XX	Stent grafts in lengths 60 – 200 mm	Nitinol, PTFE, and various plastics (PEEK, polyimide, pebax, etc.)	Yes	No	Yes

The materials used to construct the LimFlow System including all components are well characterized with a long history of clinical use in, and similar in form to, approved and marketed medical devices. The LimFlow System contains no medicinal products, human and/or animal tissues or their derivatives, or other biologically active substances.

2.5. Traceability

Traceability shall be achieved during the clinical investigation by assignment of lot or serial numbers on all LimFlow System components. Catalogue numbers and lot or serial numbers of all devices used will be collected and recorded on the Case Report Forms (CRFs). LimFlow SA will supply the device; any requests for additional materials,

equipment, service, or information shall be directed to LimFlow SA. An inventory of materials will be taken at monitor site visits.

2.6. Device description

The LimFlow System comprises the following five (5) components:

- **Ultrasound system**

The LimFlow ultrasound system consists of a power supply, a laptop computer, and a transceiver box. The system produces a short electrical pulse which is applied to the transmit catheter. The signal received by the receive catheter is amplified, filtered, and digitized. The received signal is then displayed on the laptop as a waveform, giving a visual display of the strength of the received pulse and hence permitting orientation of the two catheters. Software running on the laptop permits the gain of the receiver and other parameters to be adjusted.

- **Extension cable set**

The LimFlow extension cables carry power between the LimFlow ultrasound system and the LimFlow arterial and venous catheters.

- **Arterial and venous catheter set**

The arterial catheter is placed over a standard 0.014" guide wire through a sheath in the femoral artery and advanced to the target artery up to the point of total arterial occlusion. The arterial catheter allows for the following:

1. **Locating** neighbouring veins via ultrasound (if applicable): a small single directed ultrasonic transmitter as its tip allows to detect the venous catheter in a neighbouring vein. The handle design and the catheter body allow for an easy torque and push-pull to find the correct location.
2. **Connecting** to a neighbouring vein by advancing a crossing-needle: the catheter has a handle which advances the crossing needle from artery to vein. The catheter is placed into the artery with the needle retracted inside the catheter shaft. A standard 0.014" guide wire can be placed through the advanced needle from the proximal hub (this wire is referred to as the "*crossing wire*").

The venous catheter acts as a target in the vein for aligning the needle of the arterial catheter via ultrasound or fluoroscopy. The catheter is placed over a standard 0.014" guide wire and is placed through a sheath in the corresponding target vein and advanced up to and parallel to the arterial catheter. The venous catheter is left in place and the arterial catheter is rotated and moved longitudinally to facilitate creation of the arterio-venous connection.

Both arterial and venous catheters are intended to be used in a catheterization laboratory in consenting patients under fluoroscopy guidance. Both catheters are supplied sterile, removed at the end of the procedure, and intended for single use only.

- **Valvulotome**

The valvulotome is intended to make venous valves incompetent. The valvulotome is a device that is inserted over the crossing wire, passing the crossing section into the venous vessel. A push-pull deployment mechanism allows to deploy a nitinol cutting basket mounted at the distal tip. This cutting element self-centres in the venous vessel up to a maximum diameter of 4.5 mm. The actual cutting blades are arranged at a lower diameter as the maximum diameter of the cutting element, this prevents cutting the venous vessel but allows cutting of the vein valves once the cutting element is pushed through the valves. The device (undeployed cutting element) has a total outside diameter of 4 Fr. The valvulotome is supplied sterile and intended for single use only.

- **Stent grafts**

To facilitate constant blood flow through the newly-created crossing from artery to vein, a stent graft needs to be inserted. The LimFlow stent grafts product line consists of different self-expanding stent graft sizes and shapes, in order to meet physiological variations in anatomy of patients, and one delivery system, which is compatible for each stent size. The blank laser-cut nickel-titanium alloy (nitinol) stent serves as a base for additional forming and electro spun PTFE encapsulation procedures to obtain a final stent graft.

The stent graft delivery system comprises of inner tubing, compatible with a 0.018" guide wire lumen and a flushing lumen, which is proximally accessible through a check valve. Design input specifications require 7-Fr sheath compatibility for the delivery device. In order to achieve excellent mechanical properties and functional pushability the outer shaft was designed with a special braid pattern. Two radiopaque markers are attached to the distal end of the delivery device where the stent is crimped in between. Unintended stent movement during sheath retraction is restricted by the delivery device.

2.7. Training and experience needed

The procedure itself should be performed by vascular surgeons and/or interventionalists experienced in interventional techniques such as complex percutaneous transluminal angioplasty and stenting in the lower limb. Study investigators will be selected based on their experience in performing below-the-knee interventions and duly trained by LimFlow SA on the percutaneous deep vein arterialization specific medical procedure. In order to avoid a learning curve bias, each study investigator will be required to first perform at least one (1) successful revascularization in a “roll-in” subject. “Roll-in” subjects will be included the study but excluded from the endpoint analysis. In addition, a LimFlow SA representative will attend the treatments performed in each site in order to assist the physician on technical issues as well as to ensure that treatment characteristics and potential complications are duly recorded.

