6.3.3. Point of enrolment

Once any component of the LimFlow System is introduced into the body, the subject will be considered to be enrolled in the study and subject to all follow-up requirements. If the device is introduced but implantation is either not attempted or unsuccessful, subjects will be followed through 30 days for safety only, or through resolution or stabilization of any device- or procedure-related adverse events, whichever is longer; those subjects will then be exited from the study and will not be replaced. In addition, "roll-in" subjects performed to avoid a learning curve bias will be included the study but excluded from the endpoint analysis. In some instances, "roll-in" subjects within the study may not be required for any study site who has performed LimFlow System procedures outside the study in the commercial setting.

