7.1. Statistical design, method and analytical procedures

Subject demographics, baseline characteristics and medical history will be summarized descriptively. Mean and standard deviation will generally be reported for continuous variables; median and range may be reported instead if the data distribution is skewed. Frequencies and proportions will be reported for categorical variables.

The design of this post-market study (PMS) is mirroring that of the early feasibility study (EFS) conducted in the United States of America, allowing for both datasets to be pooled in order to perform a statistical analysis on a larger cohort of patients.

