7.5. Treatment of missing, unused, or spurious data

The number of missing data will be presented for each variable as part of the descriptive statistical analysis. Subjects withdrawn and/or lost to follow-up will be presented in a patient tree showing detailed patient accountability at each follow-up visit.

8. Data management

Electronic Case Report Forms (eCRFs) will be specifically developed on the [IBM Clinical Development](#) platform for the study. The eCRFs will be used for data collection during the course of the study and must be completed for all patients enrolled into the study. It is the responsibility of the investigator to ensure the quality of the data collected and recorded in the eCRFs. The eCRFs will be reviewed for errors, omissions, internal consistency, and to ensure that the investigator has signed and dated the appropriate sections; entered data will be audited for verification and validation purposes.

Data collection will include clinical data, as well as medical images based on the clinical endpoints outlined above. Images will be centrally analysed by the independent committee. Specifically, the role of the core laboratory will be (1) to assess the anatomical eligibility of all candidates at baseline and (2) to assess the safety endpoint at follow-up timepoints.

The eCRFs are compliant with FDA 21 CFR Part 11 requirements. All information and data concerning patients or their participation in this study will be considered confidential. Only authorized personnel will have access to this confidential information. All data used in the analysis and reporting of this evaluation will be without identifiable reference to individual patients. Patients will be identified using a six-character sequence (ISO 3166-1 α-2 country code; two-letter site code; two-digit patient number).

The investigator must retain paper copies of study records. LimFlow SA will maintain copies of correspondence, data, and other records related to the study. LimFlow SA will maintain records related to the signed Investigator's Agreements.

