Stroke	A stroke is any sudden development of neurological deficits, such as vertigo, numbness, aphasia, or dysarthria due to vascular lesions of the brain such as haemorrhage, embolism, thrombosis, or rupturing aneurysm.
Success	Technical success is defined as completion of the endovascular procedure and immediate morphological success with successful placement of the arterial and venous catheters in the desired location in the limb, and ability to place the stent graft. Procedural success is defined as combination of technical success, and absence of all-cause death, above-ankle amputation or clinically driven major re-intervention of the stent graft.
Survival	Freedom from all-cause mortality.
Thrombosis	Formation or development of a blood clot or thrombus, specifically in the arterial or venous system of the ipsilateral distal extremity.
Transient Ischaemic Attack (TIA)	Focal neurologic abnormalities of sudden onset and brief duration that reflect dysfunction in the distribution of the affected artery. Transient ischaemic attack is characterized by fully reversible symptoms of short duration.

19. Bibliography

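### Roll-in patients drop out of every endpoint under a label that depends on procedural outcome; report all treated subjects beside the planned analysis cohort

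*Combined protocol and SAP*

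**What the plan says.** Section 2.7 sets the roll-in rule by investigator: "each study investigator will be required to first perform at least one (1) successful revascularization in a" roll-in subject. The stated purpose is to avoid a learning-curve bias. Sections 2.7 and 6.3.3 both exclude roll-in subjects from the endpoint analysis ("subjects will be included the study but excluded from the endpoint analysis"), and neither excepts any endpoint. Sections 1.6.2, 6.1.1 and 6.3.5 give up to 25 subjects: roll-ins plus 20 for analysis.

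Section 6.3.3 enrols a subject once any device component enters the body; from then on "the subject will be considered to be enrolled in the study and subject to all follow-up requirements". If implantation is not attempted or fails, follow-up is for safety only, through 30 days or until related events settle if that is longer; "those subjects will then be exited from the study and will not be replaced". The section does not say whether such a subject counts as roll-in or analysis. It adds that roll-ins "may not be required for any study site who has performed LimFlow System procedures outside the study", which is an exception by site.

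Section 18 defines technical success ("Technical success is defined as completion of the endovascular procedure and immediate morphological success", with further conditions) and procedural success. It links neither to the success that ends roll-in.

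Section 7 names no analysis set and plans no endpoint summary for all treated subjects. Section 7.1 describes the US feasibility study as a mirror design, "allowing for both datasets to be pooled in order to perform a statistical analysis on a larger cohort of patients". Under section 8, eCRFs "must be completed for all patients enrolled into the study".

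**The concern.** The study aims at real-life data (5.1) from consecutive patients (6.1.2). In a descriptive single-arm study, the choice of denominator is a large part of the result. Here the denominator omits the first cases, and the boundary is set by outcome. If a failed first case stays roll-in, the next case becomes roll-in because of that failure. If only the successful case is the roll-in, the failed case is analysed because of its own failure.

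The study is open-label, a sponsor representative attends the procedures (2.7, 6.4.3), and interim analyses may take place at any time (7.3). An unstated class for a failed first case could therefore be settled after its result is known. Deaths, major amputations and failed procedures among first cases would not enter AFS, limb salvage or success, and no planned table would show how much that matters.

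**Working it through.** **1. The plan's own figure.** 25 − 20 = 5 roll-ins at most, and 5/25 = 20%. The figures agree with each other. Section 7.2 says the sample size was not derived statistically, so there is no power or precision calculation to reproduce.

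**2. Which reading the text favours.** In section 2.7, the word *first* places the success before any analysis case, and *at least one* allows several roll-ins. A failed first case therefore most naturally stays roll-in. The no-replacement rule in 6.3.3 could suggest that it uses an analysis place, but that rule covers any unsuccessful implant and does not mention roll-in.

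**3. Stop-at-success effect under the natural reading.** The documents give no number of investigators and no success rates, so both are assumed. The simulation used 60,000 runs per scenario and four operators, with cases assigned at random, stopping at 20 analysis or 25 treated subjects. AFS gap = success gap × (AFS after success − AFS after failure), with assumed AFS of 0.75 after success and 0.35 or 0.15 after failure (differences 0.40 and 0.60). Gaps are in percentage points, from unrounded rates.

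| Assumed success rate | Analysis cohort | All treated | Success gap | AFS gap |
|---|---|---|---|---|
| 0.90 throughout | 0.900 | 0.900 | 0 | 0 |
| two operators 0.95, two 0.80 | 0.876 | 0.875 | 0.15 | 0.06–0.09 |
| two 0.95, two 0.60 | 0.786 | 0.775 | 1.06 | 0.42–0.64 |
| two 0.95, two 0.40 (extreme) | 0.713 | 0.675 | 3.85 | 1.5–2.3 |
| first case 0.7, later 0.9 | 0.900 | 0.867 | 3.24 | 1.3–1.9 |

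The gaps in rows 2 to 4 arise because weaker operators lose more cases to roll-in. The last row is different. A fixed one-case roll-in gives nearly the same result: all treated = (4 × 0.7 + 20 × 0.9)/24 = 20.8/24 = 0.867, against 0.90 analysed. That gap comes from excluding first cases at all, not from the success wording.

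**4. The other reading (failed first case analysed).** Take 24 treated, with each of four operators giving up one success as roll-in:
- Constant 0.90: (24 × 0.90 − 4)/20 = 17.6/20 = 0.88, against 0.90 in all treated.
- Constant 0.80: (24 × 0.80 − 4)/20 = 15.2/20 = 0.76, against 0.80.
- First case 0.7, later 0.9: (20.8 − 4)/20 = 0.84, against 0.867.

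Each case moved changes a rate on 20 subjects by 1/20 = 5 points.

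**5. Bounds that need no success rate.** Suppose the analysis cohort shows 14/20 = 70% (illustrative; exact 95% CI 46% to 88%). All-treated AFS then lies between:
- 14/23 = 61% and 17/23 = 74% with 3 roll-ins;
- 14/25 = 56% and 19/25 = 76% with 5 roll-ins.

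**6. Missing 12-month outcomes.** At an assumed success rate of 0.90, about 2.4 of 24 treated subjects would have an unsuccessful implant and could exit early under 6.3.3. With 25 treated, each one widens a best-case/worst-case AFS range by 1/25 = 4 points. Censoring them at exit is informative. On the assumptions in step 3, true AFS is 0.9 × 0.75 + 0.1 × 0.35 = 0.71, or 0.9 × 0.75 + 0.1 × 0.15 = 0.69. Censoring could show up to about 0.75, which is 4 to 6 points too high.

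**The case against.** Excluding roll-ins is planned openly, justified as protection against a learning curve, and built into the cohort size. The study tests no hypothesis (7.2), so no decision threshold is at risk. Under the natural reading the stop-at-success bias is near nil unless operators differ greatly, and the bounds of 56% to 76% lie inside the sampling interval of 46% to 88%. All of this stands.

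A reader might infer that the rule materially inflates the reported results, and might cite 0.90 against 0.84 for the success rate. The documents do not support that: the swing needs the less natural reading together with an assumed learning curve. A reader might also infer that roll-in safety is lost. It is not: adverse events are recorded and adjudicated without a roll-in exception (14.2).

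It can also be said that all-treated data will be incomplete. That is true for 12-month outcomes after an unsuccessful implant, but not for roll-ins with a successful implant, who remain in follow-up.

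The objection does not remove the main point. The plan contains nothing that would show whether early results were worse, and it leaves the label of a failed first case open.

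**Conclusion.** The point holds as a cheap improvement of modest weight. Up to 5 of 25 treated patients (20%) are absent from AFS, limb salvage, patency, wound healing and success, under a label that turns on outcome, and no all-treated result is planned. The 20% applies if 20 analysis subjects are reached and all five further places are used.

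The stop-at-success rule itself adds 0 to about 1 point to the success rate, and more only if operators differ greatly. The larger issue is visibility: an illustrative 70% in the analysis cohort leaves 56% to 76% open for all 25. Operator number, success rates and AFS rates are assumptions, and the documents do not show how many roll-ins or failed first cases occurred.

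The documents do not support calling the exclusion an error or the planned main analysis invalid. They also do not show whether five roll-in places are enough. The link to a section 18 success term, the pooled set and the site/investigator wording are clarifications only.

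**What to change.** 1. Keep the planned analysis cohort. Beside it, report AFS and each secondary endpoint for all treated subjects, with the denominator stated, and list roll-in cases by sequence and result. Give the number exited early after an unsuccessful implant, and show all-treated 12-month AFS as a best-case/worst-case range. Do not rely on censoring at exit.
2. For analysis purposes, record roll-in status in the eCRF before each remaining procedure, independently of its result. State how failed first cases already treated are classed before endpoint data are analysed. The training requirement in 2.7 is unchanged.
3. As minor clarifications, tie the success that ends roll-in to a section 18 term, reconcile the per-investigator wording in 2.7 with the per-site exception in 6.3.3, and state which set enters the pooled analysis.

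Cost: protocol and SAP wording with ethics committee review, one extra set of tables and a listing; no added patients or visits. All-treated rates may be slightly less favourable, and some 12-month outcomes will be missing for failed implants. Enrolment was expected to finish by the end of October 2022 (6.3.5), so prospective labelling may reach few cases. Item 1 and the classing of past failed cases would still apply.
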